In the phase 1 study, administration of the drug was briefly suspended in 7 of 13 patients because of grade 3 abnormalities on liver function testing (n=2) or grade 3 or 4 mucositis (n=5). Liver-function abnormalities did not recur when the drug was re-started. The adverse event profile was similar to the expected toxicity observed in patients undergoing reduced intensity conditioned SCT without maraviroc. In addition, there were no viral or fungal infections other than asymptomatic reactivation of cytomegalovirus. The incidence of bacterial infections was not higher than the expected rate for a reduced intensity transplant. In conclusion, Maraviroc was generally well tolerated in this study [30,31].

Research Plan

The study continues seamlessly from one stage to the next and therefore does not have “phases” in the conventional sense. The initial part of the study will be a dose finding and feasibility study. The second stage of the study will involve administering the appropriate dose of Maraviroc to children as a prophylactic agent against acute graft versus host disease. Maraviroc will be added to standard GVHD prophylaxis of a calcineurin inhibitor (cyclosporine or tacrolimus), methylprednisolone, mycophenolate mofetil (MMF) or methotrexate. The study plan is described below.

Number of Subjects

We plan to enroll 65 patients over the course of approximately 5 years.

Selection

This study will be conducted at Cincinnati Children’s Hospital, in patients 2 years of age-40 years of age who are undergoing allogeneic stem cell transplant.

Eligibility

Inclusion Criteria

1. Ages- 2 years and \leq 40 years. For Phase I, the dose finding part of the study, enrollment will be limited to ages 2-12 years as adult dosing is already available and it is likely that a teenager metabolizes the drug similar to adults.

2. All diagnoses are eligible
3. Stem cell source must be marrow, peripheral blood stem cells or cord blood from an unrelated or related donor
4. All conditioning regimens are eligible.
5. Patient must be planned to receive a calcineurin inhibitor (cyclosporine or tacrolimus) together with steroid, methotrexate or mycophenolate mofetil as GVHD prophylaxis.
6. Willingness and ability to provide signed informed consent (including assent, for ages 11-17 years)

Exclusion Criteria

1. Documented anaphylaxis to Maraviroc
2. Ex vivo T depleted grafts

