All patients in phase I treated at the established dose as well as patients treated at a lower dose yet achieve a therapeutic pharmacokinetic level will be included in further analysis. The historical incidence rate of GVHD in pediatric patients undergoing allogeneic stem cell transplantation with GVHD prophylaxis agent of a calcineurin inhibitor+ methylprednisolone is 16% (BMT 2012 data at CCHMC). Assuming the incidence rate for patients treated at the dose established in phase I is 6% then a sample size of evaluable 65 patients provides an 80% power of detecting a difference between this rate and the historical incidence rate. This sample size determination was computed using a two-sided binomial test.

The exact two-sided 95% confidence intervals for the day 100 incidence rate of grade GVHD will be reported. For time-to-event endpoints, e.g., overall survival and time to occurrence of GVHD, we will present Kaplan-Meier curves and corresponding survival p-values will be computed using log-rank tests. Demographic information such as age and race will be tabulated. Descriptive statistics, including means, standard deviations, and ranges for continuous parameters, as well as frequencies for categorical parameters, will be presented

Regulatory Issues-

The protocol and informed consent document for this study will be approved in writing by the Institutional Review Board (IRB) prior to any patient being registered on the study.

Changes to the protocol, as well as a change of study staff, must also be approved by the IRB. Records of the Institutional Review Board review and approval of all documents pertaining to this study must be kept on file by the investigator and are subject to FDA inspection at any time during the study.

Informed consent will be obtained prior to the treatment of participants.

This protocol will be performed under an investigator-initiated IND.

Study Monitoring and Auditing:

Monitoring and auditing procedures will be followed to ensure that the study is conducted, documented, and reported in accordance with the IRB approved protocol, all applicable federal regulations and guidelines, and applicable regulatory requirements of Cincinnati Children's Hospital Medical Center.

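### The 16% benchmark is an observed centre rate of unstated size, but the test and power statement treat it as a known constant and no planned analysis carries its sampling error

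*Combined protocol and SAP*

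**What the plan says.** All figures are in the Statistical analysis section of the combined protocol and SAP. The primary efficacy objective is to test the day-100 rate of any GVHD against a historical rate. That rate "is 16% (BMT 2012 data at CCHMC"; no count, cohort size or interval accompanies it.

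With 6% assumed on maraviroc, the section says that "a sample size of evaluable 65 patients provides an 80% power of detecting a difference between this rate and the historical incidence rate". On method it adds: "This sample size determination was computed using a two-sided binomial test". No significance level is given.

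The only interval planned for this endpoint concerns the trial's own rate: "The exact two-sided 95% confidence intervals for the day 100 incidence rate of grade GVHD will be reported". The study has one arm (65 patients, Number of Subjects). No section gives a range for the benchmark, a sensitivity analysis on it, or a comparison that uses the historical patients as a sample.

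**The concern.** The plan words its claim as a difference from the centre's historical incidence. The 16% is an observed proportion with its own sampling error, even if the historical patients match the trial patients perfectly. A one-sample binomial test measures distance from the number 0.16, and its error rate and power refer to that number.

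With no concurrent control, the efficacy conclusion rests on this one figure. If the centre's true rate was well below 16%, a trial result near 6% could reflect little or no improvement and still be reported as significant. A reader of the results could not judge this, because the plan neither gives the size of the historical cohort nor commits to an analysis that uses it.

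**Working it through.** **Inputs.** From the Statistical analysis section: n = 65, p0 = 0.16, p1 = 0.06, two-sided binomial test. Assumed: alpha = 0.05 two-sided, inferred from the 95% CI; historical cohort size m = 50, 100, 150 or 200, since none is given. The 2012 label is read as one year's transplants.

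**Step 1: the plan's own figure.** X is the number of GVHD cases among 65.

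- P(X ≤ 4 | 0.16) = 0.0153 and P(X ≤ 5 | 0.16) = 0.0401. With 0.025 in the lower tail, benefit is declared at ≤ 4/65.
- Power at 6%: P(X ≤ 4 | 0.06) = 0.649. The stated 80% is not reproduced.
- A one-sided 5% test rejects at ≤ 5/65, and P(X ≤ 5 | 0.06) = 0.806.
- Normal approximation, n = [(z_α√(p0q0) + z_β√(p1q1)) / (p0 − p1)]². One-sided: [(1.645 × 0.3666 + 0.8416 × 0.2375) / 0.10]² = 64.5, so 65. Two-sided, with 1.960: 84.3, so 85.

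The stated 65 patients and 80% therefore match a one-sided 5% test. For the test as described, the power against an exact 16% is about 65%.

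**Step 2: error in the benchmark.** The exact (Clopper-Pearson) 95% CI for 8/50 is 7.2–29.1%, for 16/100 9.4–24.7%, for 24/150 10.5–22.9% and for 32/200 11.2–21.8%.

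**Step 3: false claims of benefit.** Let both true rates be 16%. Draw the historical count h from Bin(m, 0.16), set the null at h/m, and let c(h) be the largest count whose lower tail is ≤ 0.025. The rate is Σ P(h) × P(X ≤ c(h) | 65, 0.16).

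**Step 4: power with both samples counted.** Fisher's exact test, two-sided 5%, X from Bin(65, 0.06), averaged over h from Bin(m, 0.16).

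| m | False claim of benefit | Power at 6%, both samples (Fisher) |
|---|---|---|
| 50 | 6.6% | 36% |
| 100 | 4.1% | 46% |
| 150 | 3.3% | 51% |
| 200 | 2.7% | 54% |
| 16% exact | 1.5% | 65% (one-sample test) |

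The false-claim rate is 2.6% at m = 250 and 2.3% at m = 300, so the excess over 2.5% is gone by about 300.

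Fisher's test is conservative, so the power loss was checked with a two-sample normal calculation: 42%, 49%, 52% and 54%, against 64% for the one-sample normal figure. The loss is not an artefact of Fisher's test.

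**Step 5: the result the trial hopes for.** 4/65 is 6.2%, and the planned test calls it a benefit. Against 8/50, 16/100 or 24/150, Fisher's p is 0.12, 0.086 or 0.050 (0.0502 unrounded); none is below 0.05.

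**Step 6: an inert drug and a lower true rate.** The ≤ 4/65 rule claims benefit with probability 9.7% if the true rate on both sides is 12%, and 20.9% if it is 10%. Both rates lie inside the interval for 16/100.

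**Sensitivity to the level.** Under the one-sided 5% rule that matches the stated power, false claims of benefit are 10.6%, 6.9%, 5.9% and 5.4% for m = 50 to 200, and 4.6% at m = 300, against 4.0% if 16% were exact.

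**The case against.** A fixed null value is the usual form of a single-arm phase I/II test, and the planned test is valid for the null it literally states: if 16% is taken as given, its lower-tail size is 1.5%. The exact CI for the trial rate can be set against any benchmark a reader prefers. The size of the problem also depends on a cohort size that the documents do not give; with several hundred historical patients it would be small. The 2012 label could mean data compiled in that year and not one year's transplants.

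Much of this stands. The fixed-16% test need not be replaced, and the inflation is conditional on cohort size. What does not stand is that the planned CI answers the point: it describes one side of a two-sided comparison, while the power sentence claims power against the historical rate itself. The missing denominator is also the reason a reader cannot dismiss the problem as small.

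**Conclusion.** The point holds as a limitation that is cheap to repair. The benchmark's sampling error is carried nowhere. For cohorts of 50 to 200 it raises the chance of a false claim of benefit over the historical rate to between 6.6% and 2.7%, and lowers power from about 65% to between 36% and 54%. These figures assume a two-sided 5% level and the stated range of cohort sizes. They cover sampling error only; whether the historical patients are comparable with the trial patients is a separate question.

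A reader might infer three stronger conclusions that the documents do not support:

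- **That the false-positive rate exceeds nominal whatever the cohort.** Cohort size is not given, the low-side excess disappears by about 300, and the test keeps its size for a literal null of 16%.
- **That the whole gap below 80% comes from the benchmark.** About 15 points (80% − 65%) are already missing with 16% exact, because the stated power matches a one-sided test and the text says two-sided.
- **That power is as low as 24%.** Fixing the historical count at 8/50 gives 24% under Fisher's test, but that depends on one count and an integer cutoff; averaged over historical sampling it is 36%.

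**What to change.** 1. Keep the test against a fixed 16%.
2. Add a supportive analysis: the difference between the trial and historical proportions, with a 95% CI that uses both samples. Report with it the numerator, denominator and exact 95% CI behind 16%, and say which transplants the 2012 label covers.
3. State the significance level and sidedness, and correct the power sentence: about 65% for a two-sided 5% exact test, or about 80% for a one-sided 5% test if that was intended. In either case say that this is power against a fixed 16% and does not allow for its sampling error. Labelling the present 80% as power against a fixed value, with the test still two-sided, would keep a wrong number.

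The cost is a few sentences and one analysis of the centre's own historical data; design, sample size and patient care do not change. The downside is a less favourable stated power if the test stays two-sided, and an interval for the difference wider than one that treats 16% as known.

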For the first part of the study, where full AUC analysis will be performed to verify the dose, we anticipate initially enrolling 12 patients to achieve 12 dose verifications. Any patients who do not achieve a complete PK data profile (i.e. due to suboptimal dose or incomplete course of study drug) will be replaced to achieve 12 dose verifications. The total number of patients will still remain 65 (Phase I and Phase II). The age of enrollment for these patients will be limited to 2-12 years old. This age restriction has been imposed because adult dosing for maraviroc in the stem cell transplant setting has already been established and it is likely that teenagers metabolize the drug similar to adults. The second part of the study, where full AUC analysis will not be conducted, will enroll the remaining patients between the ages 2-40 years.

We will enroll eligible patients and maraviroc will be administered as per study rules. Area under the concentration-time curve (AUC) determination will be performed on days 0 +/- 3 days and 10 +/- 3 days to account for weekends, national holidays or clinical deterioration not allowing for scheduled blood draws on the specified days. PK analysis will be performed after the first 3 patients. As per our study design graph, this is not an "interim" analysis, but an analysis to verify PK target attainment which then will drive either further observation or dose escalation. See Figure 1.

[figure not shown]

Figure 1. Study design

Pharmacokinetic measurement and analysis-

Blood for PK will be collected on day 0 +/- 3 days and Day 10 +/- 3 days. Complete PK profile (full AUC) will be performed on these days (see time points below). Evaluation of maraviroc trough levels will also be done routinely on all patients on study on days 0,7,14 and 21 in order to collect additional PK data, verify compliance and allow for additional dose corrections if necessary.

Target AUC/12 hours= $\geq 100\text{ng/mL}$ (based on HIV data)

PK processing will be performed at University of North Carolina's Clinical Pharmacology and Analytical Chemistry Laboratory using mass spectrometer with HPLC separation.

Plasma Maraviroc concentration data will be analyzed by compartmental and non-compartmental analysis with the help of [name], Director of Pediatric Pharmacology Research Unit (PPRU) at CCHMC, and parameter estimates generated will include clearance, half-lives, and volume of distribution along with area under the curve (AUC).

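### No significance level is stated for the primary test; at the two-sided 5% implied by the planned 95% interval, 65 patients give about 65% power, not 80%

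*Combined protocol and SAP*

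**What the plan says.** The Statistical analysis section makes testing the 100-day incidence of any GVHD against a historical rate a primary objective. The historical rate is 16%, the assumed rate at the phase I dose is 6%, and the section states that a "sample size of evaluable 65 patients provides an 80% power of detecting a difference between this rate and the historical incidence rate". It adds: "This sample size determination was computed using a two-sided binomial test". No alpha, p-value threshold or rejection boundary appears anywhere in the document.

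The one level given for this endpoint is in the next paragraph: "The exact two-sided 95% confidence intervals for the day 100 incidence rate of grade GVHD will be reported".

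On numbers, the Number of Subjects section says "We plan to enroll 65 patients over the course of approximately 5 years", and the Study design section holds the combined phase I and phase II total at 65 even when patients with incomplete PK profiles are replaced. The Statistical analysis section carries forward phase I patients treated at the established dose, and adds that "patients treated at a lower dose yet achieve a therapeutic pharmacokinetic level will be included in further analysis". It does not define *evaluable*.

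**The concern.** A power figure means nothing without the alpha it was computed at. Here the reader must infer alpha, and the two available clues disagree: the 95% interval points to two-sided 5%, while the 80% power points to a looser level. If two-sided 5% applies, the trial has about a 35% chance of missing the effect it was designed to find, rather than 20%.

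The success criterion is also open. One plausible result, 5 cases in 65, is a success under the rule that delivers 80% power and a failure under the planned interval. In a single-arm trial with a fixed historical comparator, that choice should not be left until the count is known.

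The sample size also leaves no room for patients who turn out not to be evaluable, because the evaluable number equals the enrolment total.

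**Working it through.** **Inputs**, all from the Statistical analysis section: null rate p0 = 0.16, alternative p1 = 0.06, n = 65, one-sample two-sided binomial test. Alpha is not given. X is the number of patients with GVHD by day 100.

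**1. Reproducing the stated 80%.** The normal approximation is

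power = Φ[ (p0 − p1 − z·√(p0(1−p0)/n)) / √(p1(1−p1)/n) ]

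The two standard errors are √(0.16×0.84/65) = 0.04547 and √(0.06×0.94/65) = 0.02946.

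- With z = 1.645 (one-sided 5%, or two-sided 10%): (0.10 − 0.0748)/0.02946 = 0.856, so power is 80.4%. The required n for 80% is 64.5, which rounds up to 65.
- With z = 1.960 (two-sided 5%): (0.10 − 0.0891)/0.02946 = 0.369, so power is 64.4%. The required n for 80% is 84.3, which rounds up to 85.

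The plan's 65 and 80% therefore match a calculation with 5% in the lower tail.

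**2. Exact binomial, n = 65.**

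| Reject low if | P under 16% | P under 6% (power) |
|---|---|---|
| X ≤ 4 | 0.0153 | 0.649 |
| X ≤ 5 | 0.0401 | 0.806 |

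Two-sided 5% allows 2.5% in the lower tail. Since 0.0401 exceeds 0.025, the boundary is X ≤ 4 and power is 64.9%. The upper rejection region (X ≥ 17) adds a negligible amount at p1 = 0.06. Equal-tailed, minimum-likelihood, mid-p and score versions of the test all give this boundary at two-sided 5%; the score p-value at X = 5 is 0.068. With 5% in the lower tail the boundary is X ≤ 5 and power is 80.6%.

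**3. The result on which the rules differ.** P(X = 5 | 6%) = 0.8059 − 0.6490 = 0.157, which is the whole gap. Exact (Clopper-Pearson) intervals:

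- 4/65, 95%: 1.7% to 15.0%, excludes 16%.
- 5/65, 95%: 2.5% to 17.0%, contains 16%.
- 5/65, 90%: 3.1% to 15.5%, excludes 16%.

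**4. Fewer than 65 evaluable.** The documents give no expected loss, so a range of 60 to 65 is assumed for illustration. Each cell gives the boundary and the exact power at 6%.

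| Evaluable n | Lower tail ≤ 2.5% | Lower tail ≤ 5% |
|---|---|---|
| 65 | ≤ 4, 64.9% | ≤ 5, 80.6% |
| 64 | ≤ 4, 66.1% | ≤ 5, 81.5% |
| 63 | ≤ 4, 67.3% | ≤ 5, 82.4% |
| 62 | ≤ 4, 68.5% | ≤ 4, 68.5% |
| 61 | ≤ 4, 69.7% | ≤ 4, 69.7% |
| 60 | ≤ 3, 51.1% | ≤ 4, 70.9% |

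Power moves in a sawtooth because the boundary is a whole number. With 5% in the lower tail, the 80% is lost once 3 of the 65 are not evaluable. The 2.5% column is for the equal-tailed test that matches the Clopper-Pearson interval, and its lower rows depend on that choice: at n = 61 the minimum-likelihood test rejects only at ≤ 3 (49.8%), and at n = 60 the score test still rejects at 4 (70.9%).

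**The case against.** The best defence is that this is an omission, not a wrong figure. At two-sided 10% every stated number agrees, including the two-sided label, and the section says only that the 95% interval will be reported, not that it decides the test. That is fair as far as it goes: two-sided 5% is an inference. But two-sided 10% is also unstated, is not what an unqualified two-sided test normally means, and conflicts with the interval planned for the same endpoint. No single conventional alpha fits both the 80% and the 95% interval under the named test.

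A second argument is that 80% can be reached at nominal two-sided 5% with a Wald z-test, which rejects at 5/65 (z = −2.51). It does, but its true size is 5.2%, above the nominal level, and it contradicts the exact interval. Strictly, the 5-case boundary needs a lower-tail alpha of at least 4.0%; one-sided 5% and two-sided 10% are the conventional levels that allow it.

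Third, the evaluability point is separate from alpha, and the section does say which phase I patients count. That stands in part. Even so, *evaluable* is undefined beyond that, the Study design section fixes the total at 65, and after a dose escalation the lower-dose patients who miss the PK level would not be carried forward.

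**Conclusion.** The concern holds, and the power statement is wrong as written. At two-sided 5%, exact power with 65 evaluable patients is 64.9%, about 15 percentage points below the stated 80%. The stated figure is recovered (80.6%) only with 5% in the lower tail. The power figures take the plan's 16% and 6% as given, and the 64.9% also rests on reading two-sided 5% from the planned 95% interval. The absence of a stated alpha needs no assumption.

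This must be settled before the efficacy data are analysed, because a result with a 15.7% probability under the planned effect changes the primary conclusion. The missing allowance for non-evaluable patients is a related but secondary gap. It matters most if the looser level is chosen.

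**What to change.** In the Statistical analysis section, state alpha, the rejection boundary and the power that follows, choosing one of:

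- **(a) Two-sided 5%.** Reject if 4 or fewer of 65 have GVHD; exact lower-tail size 1.5%, power about 65%. This agrees with the planned 95% interval.
- **(b) One-sided 5%, or two-sided 10%, which has the same low-side boundary.** Reject if 5 or fewer of 65; exact lower-tail size 4.0%, power 80.6%. Report a one-sided 95% upper bound or a two-sided 90% interval to match.

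The choice should be made without knowledge of the accruing GVHD count. The first stopping rule already looks at visceral GVHD in the first 20 subjects, so adopting the looser boundary late would be hard to defend.

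Also define *evaluable*, and tabulate the boundary and power for each evaluable number from 60 to 65, naming the test used.

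The cost is one paragraph and no extra patients. Under (a) the stated power falls to about 65%. Under (b) the reported interval changes, and so does the two-sided label if one-sided 5% is declared. Only if the sponsor wants 80% at two-sided 5% does the sample size change: exact power first reaches 80% at n = 78 (81.3%) and, for the equal-tailed test, stays there from n = 95.

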 - c. Other grade 4-5 toxicity , unless clearly related to stem cell transplant and not to study drug, including but not limited to veno-occlusive disease of the liver, acute graft versus host disease, autoimmune cytopenias, infectious complications due to stem cell transplant, or organ toxicities due to conditioning regimens.

BSA	Original Dose	Dose escalation	Value increment/dose
<0.22	40 mg bid	50 mg bid	+ 10 mg
0.2-0.43	100 mg bid	120mg bid	+ 20 mg
0.44-0.72	200 mg bid	250 mg bid	+ 50 mg
0.73-1.19	300 mg bid	350 mg bid	+ 50 mg
1.20-1.30	300 mg bid	350 mg bid	+ 50 mg
1.31-1.73	300mg bid	350 mg bid	+ 50 mg
>1.73	300 mg bid	350 mg bid	+ 50 mg

Table 4. Table showing doses and increments for dose escalation of Maraviroc.

Stopping Rules

1. If the incidence of Grade 2-4 acute GI or Liver (visceral) graft versus host disease is greater than 50% in the first 20 subjects by day +100, the study will be stopped. Enrollment will not stop while the analysis is being conducted.

2. If 3 out of 6 subjects experience DLT by day +30 as defined above at the initial dose in the first phase (AUC analysis) of the study, the study will be stopped. Enrollment will not be suspended while the analysis is being conducted.
3. The study will be halted for any grade 4 liver toxicity occurring within 30 days of study drug administration and without clear attributable alternative cause. Enrollment will be suspended while an analysis of the toxicity is being conducted. Enrollment will only restart with approval of the Medical Monitor, IRB and FDA. (Of note: any grade 3 liver toxicity (ALT > 5xULN or Total Bilirubin > 3xULN), regardless of cause, will lead to permanent discontinuation of Maraviroc for that specific patient, but enrollment will continue.)

Primary study end points

1. Feasibility
2. GVHD incidence by day +100 (all grades)
3. pK target >100ng/ml

Secondary Study end points

1. Overall survival by day +100
2. Graft failure by day + 100
3. Primary disease relapse by day +100
4. Incidence of toxicities either due to drug or transplant
5. Infectious complications which include asymptomatic viremias for EBV, Adenovirus, CMV, and/or viral disease, bacterial and fungal infections as documented by blood cultures.
6. Time to neutrophil and platelet engraftment

GVHD will be graded according to IBMTR criteria as shown in table 5 [33]-

	Stage 0	Stage 1	Stage 2	Stage 3	Stage 4

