Skin	No rash	Rash < 25% BSA	Rash 25-50% BSA	> 50% BSA or generalized erythroderma	Bullae or desquamation
GI	< 500 ml diarrhea	501-1000 ml diarrhea/day	1001-1500 ml diarrhea/day	> 1500 ml diarrhea/day	Abdominal pain and ileus
Liver	Bilirubin < 2 mg/dL	2.1-3 mg/dL	3.1-6 mg/dL	6-15 mg/dL	> 15 mg/dL

Grading		Grade 1	Grade 2	Grade 3	Grade 4
Skin		1	2	3	4
GI		0	1-2	3	4
Liver		0	1-2	3	4

Table 5. Grading and staging of GVHD.

Diagnosis of GVHD is mostly clinical and as such will be on the discretion of the treating physician. Biopsies may aid the diagnosis whenever clinically indicated but are not required in the study.

Clinical Data to be Collected and Reported:

Patients' medical information will be systematically and prospectively collected as is usual for all SCT patients. The data collected will include, but not be limited to-

1. Demographics including age, gender, weight, and height.
2. Underlying diagnosis
3. Specifics of HCT (preparative regimen, type of graft, cell dose, GVH prophylaxis, HLA type and donor relation etc.).
4. Details of engraftment (timing, failure to engraft, loss of graft)
5. Adverse effects directly related to maraviroc and transplant course
6. Onset of GVHD, grade, organ involved and treatments used by day +100
7. Whole blood donor chimerism
8. Infectious complications which include asymptomatic viremias for EBV, Adenovirus, CMV, and viral disease, bacterial and fungal infections as documented by blood cultures or bronchoalveolar lavage cultures/PCRs.
9. Overall survival at day +100
10. Incidence of relapse of primary disease by day +100

Study calendar

All testing below is part of standard evaluation for all patients undergoing allogeneic stem cell transplant and is not dependent on study enrollment, unless marked by “*”

	Enrollment	D-3	D 0 (± 3 days)	D +7 (± 2 days)	D+10 (± 3 days)	D+14 (± 3 days)	D+21 (+ 3 days)	D+30 (+ 7 days)	Monthly after day +30 until day+ 100 (± 7 days)
Informed Consent*	x								
History and physical examination	x	x	x	x	x	x	x	x	x
GVHD prophylaxis	x	x	x	x	x	x	x	x	x
CYP3A4 enzyme inducers or inhibitors *	x	x	x	x	x	x	x	x	
Acute GVHD evaluation and treatment								x	x
Full AUC analysis (dose verification part)*			X		X				
pK trough*			X	x		x	x		
pD*	X		X			X			
LFTs/CBCD/ Renal profile	x	x	x	x	x	x	x	x	x
Adverse event evaluation*		Continuous							
Compliance*		x	x	x	x	x	x	x	
Chimerism(whole blood)								x	Day + 100
Survival									Day + 100

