Maraviroc is not known to significantly affect any metabolic pathway. However, inhibitors and inducers of the cytochrome P450 metabolic pathway affect its drug level. Generally, patients in this trial will receive prophylactic antifungals as directed by their attending physician, which may include either micafungin or ambisome. Other concomitant medications are allowed except for strong inducers or inhibitors of the cytochrome P450, such as voriconazole, phenytoin, carbamazepine and rifampin. (See table 2).

Should there be emesis within 30 minutes of taking maraviroc, the drug should be re – administered. However, any emesis after 30 minutes of taking maraviroc will not require the drug to be readministered.

Risk to unborn fetus-

It is recommended that patients on study utilize appropriate methods of contraception to prevent getting pregnant or fathering a child as the effects of maraviroc on the unborn fetus is unknown. All female patients routinely undergo a pregnancy test as part of pre bone marrow transplant evaluation and only proceed with transplant when it is confirmed that they are not pregnant. Therefore we will not repeat this test prior to starting maraviroc.

Risk associated with blood draws-

This study will require research blood to be drawn as specified time points as shown in the study calendar. This blood will be drawn from a central line whenever possible and will be combined with routine clinical blood draws whenever possible and will not exceed maximum allowed blood volume for that patient per day per standard of care.

Statistical analysis

The primary objectives of this phase I/II clinical trial are to establish a therapeutic dose of Maraviroc and test the 100 day incidence rate of any GVHD in pediatric patients undergoing allogeneic stem cell transplantation against a historical incidence rate.

Phase I will consist of the determination of a therapeutic dose. A dose escalation procedure outlined in the study design will be conducted until a dose which yields 2 of 3 patients with AUC > 100ng/ml and no drug related toxicities.

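### The log-rank p-values have nothing to compare in this one-arm trial, and Kaplan-Meier overstates the probability of GVHD when patients die without it

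*Combined protocol and SAP*

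**What the plan says.** The Statistical analysis section states the primary aim as to "test the 100 day incidence rate of any GVHD in pediatric patients undergoing allogeneic stem cell transplantation against a historical incidence rate". The historical GVHD rate "is 16% (BMT 2012 data at CCHMC"; it is one percentage, with no number of patients and no curve over time. The same section gives the day-100 analysis: "The exact two-sided 95% confidence intervals for the day 100 incidence rate of grade GVHD will be reported".

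A separate sentence covers the time-to-event analyses. It opens "For time-to-event endpoints, e.g., overall survival and time to occurrence of GVHD" and continues "we will present Kaplan-Meier curves and corresponding survival p-values will be computed using log-rank tests". It names no groups, strata or reference population, and it does not say what happens to a patient who dies without GVHD.

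The Secondary Study end points list begins with "Overall survival by day +100". The data to be collected include "Onset of GVHD, grade, organ involved and treatments used by day +100", and survival status at day +100. No competing-risks analysis is planned for this trial. Cumulative incidence appears only in the account, under Previous Work Done in this Area, of the earlier adult maraviroc study.

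**The concern.** There are two separate faults in one sentence.

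- **The test.** A log-rank test compares the event experience of two or more groups, or of one group against a complete reference survival curve. This trial has one arm and the plan supplies neither. The log-rank test is the only test planned for overall survival, the first secondary end point. Any p-value eventually reported would therefore rest on groups or a curve chosen later, possibly with the data in view.
- **The estimator.** A patient who dies without GVHD can no longer develop it. Kaplan-Meier with such deaths censored treats these patients as still able to develop GVHD at the same rate as the survivors, and this inflates 1-KM. A day-100 value read off that curve could differ from the day-100 incidence in the same report, and the plan offers the reader no explanation. Relative to the true cumulative incidence, the error makes the drug look slightly worse.

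**Working it through.** The plan gives no figure for these time-to-event analyses, so there is none to reproduce. The check takes the test first and then the estimator.

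**1. Can the log-rank test be computed?**

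| What a log-rank test needs | What the plan supplies |
|---|---|
| Two or more groups | One arm; no subgroups assigned to this test |
| Or a patient-level historical cohort | None stated |
| Or a reference curve (one-sample version) | One GVHD percentage, 16%; no historical survival figure for overall survival |

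The one-sample version uses Z = (O − E)/√E, where O is the observed number of events and E is the sum over patients of the reference cumulative hazard up to each patient's last time at risk. E needs the whole reference curve. If a constant hazard reaching 16% at day 100 is assumed, the daily hazard is −ln(0.84)/100 and the test runs. In 40,000 simulated trials of 65 patients with no competing deaths, its size was 5.0% and its power against 6% was 64.5%. That curve is an assumption made for this check; the plan contains none. For overall survival there is not even a single percentage to build one from.

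**2. How far does 1-KM overstate GVHD if deaths are censored?**

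Inputs:
- g, the true day-100 cumulative incidence of GVHD: 6% (planning assumption) and 16% (historical rate), both from Statistical analysis.
- d, death without GVHD by day 100: not in the documents, assumed 2% to 20%.

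With constant cause-specific hazards, the total cumulative hazard to day 100 is H = −ln(1 − g − d). The GVHD share is H·g/(g + d), and 1-KM = 1 − exp(−H·g/(g + d)).

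Worked case, g = 0.16 and d = 0.20: H = −ln(0.64) = 0.4463; the share is 0.4463 × 0.16/0.36 = 0.1983; 1-KM = 1 − exp(−0.1983) = 0.180.

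If every death without GVHD came before every GVHD onset, the overstatement would reach its maximum, with 1-KM = g/(1 − d).

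| d (assumed) | g = 6%: 1-KM | g = 6%: maximum | g = 16%: 1-KM | g = 16%: maximum |
|---|---|---|---|---|
| 2% | 6.06% | 6.12% | 16.2% | 16.3% |
| 5% | 6.16% | 6.32% | 16.4% | 16.8% |
| 10% | 6.33% | 6.67% | 16.9% | 17.8% |
| 15% | 6.51% | 7.06% | 17.4% | 18.8% |
| 20% | 6.71% | 7.50% | 18.0% | 20.0% |

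A simulation at N = 65 (8,000 runs per setting) agrees. For g = 16% and d = 20%, mean 1-KM was 18.0% against a mean crude proportion of 16.0%. For g = 6% and d = 10%, it was 6.4% against 6.0%.

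**3. What if deaths are counted as events instead?** The curve then estimates GVHD or death, g + d. With g = 6% and d = 10%, that is 16%. This also exceeds the probability of GVHD.

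**4. Comparison with sampling error.** The exact (Clopper-Pearson) 95% interval at N = 65 is 1.7% to 15.0% for 4 events (6.2%) and 7.6% to 26.5% for 10 events (15.4%). The overstatement in the table is small beside these widths.

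**The case against.** The strongest reply on the test is that the comparator is unnamed rather than impossible. The centre's own 2012 data supplied the 16%, so a patient-level cohort may exist. Donor type, graft type and conditioning regimen are all collected and could define groups. That is fair as far as it goes, but the plan assigns none of these to the log-rank test. Naming one in advance would cure the fault; choosing one afterwards would not.

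On the estimator, several points are well taken:

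- The overstatement with censoring arises only when a death without GVHD precedes a later GVHD onset, and the plan does not actually say that deaths will be censored. The other usual choice, counting them as events, also fails to estimate GVHD probability.
- The plan does not promise a day-100 value read off the curve, and time to GVHD is not a listed end point. The conflict between two day-100 figures is therefore possible, not certain.
- The size is modest. One patient in 65 is 1.5 percentage points. At a true 6% the constant-hazard overstatement (at most 0.7 points) is less than half a patient. At a true 16% it reaches one patient only when about 16% die without GVHD.
- The plan does not say how the historical 16% was calculated. If it was itself a 1-KM figure, the direction of the error relative to that benchmark is unclear.

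These points limit the weight of the second fault. They do not make Kaplan-Meier the right estimator for GVHD, and they leave the first fault untouched.

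**Conclusion.** The concern holds. As written, the log-rank p-values for overall survival and time to GVHD are undefined; this conclusion rests on no assumed rate. Kaplan-Meier is suitable for overall survival but not for the probability of GVHD.

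With deaths censored and constant hazards, the overstatement is about 0.1 to 0.7 points at a true 6% and 0.2 to 2.0 points at a true 16%, for an assumed 2% to 20% dying without GVHD. Without the constant-hazard assumption it could reach 1.5 and 4.0 points at the top of that range. It is near zero if few patients die without GVHD.

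The sample size, the day-100 binomial test and its exact interval do not use these curves and are unaffected. This is a fault in the supporting analyses that should be corrected, not a threat to the primary conclusion.

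**What to change.** Replace the time-to-event sentence in Statistical analysis with text that does the following:

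- For time to GVHD, report the cumulative incidence function with death without GVHD as a competing event, with a day-100 estimate and 95% confidence interval, and state how graft failure is treated.
- For overall survival, keep the Kaplan-Meier curve with a 95% confidence interval.
- Delete the log-rank p-values. If the sponsor wants a comparison, the alternative is to name the groups, historical cohort or reference curve before the data are examined.
- Beside the day-100 GVHD count, report the number of patients who died before day +100 without GVHD.

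With every patient followed to day 100 or death, the day-100 cumulative incidence equals the simple proportion with GVHD, so the curve and the binary result will agree.

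The cost is one or two sentences of analysis text and standard software. No new data are needed, because GVHD onset and survival to day +100 are already collected.
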